6.6 Changes in the Conduct of the Clinical Investigation

Not applicable. No protocol amendments will be generated at any time during the investigation.

7 DATA QUALITY ASSURANCE

7.1 Study Conduct

Before implementation of the study, a meeting with all Investigators involved in the study will be arranged in order to ensure the comprehension of study protocol and procedures.

During the site initiation visit all study procedures will be detailed to the Study Staff. A science graduate monitor of High Research s.r.l. periodically visited the Investigators to ensure that the study will be conducted according to the protocol and to perform source data verification on all eCRFs filled in until the visit day.

7.2 Study Monitoring

At regular intervals during the clinical investigation, the site will be contacted, through monitoring visits, letters or telephone calls, by a representative of the monitoring team of High Research s.r.l. to review investigation progress, Investigator and patient compliance with clinical investigation protocol requirements and any emergent problems. These monitoring visits included but will be not limited to review patient informed consent, patient recruitment and follow-up, AE and SAE documentation and reporting, medical device administration, medical device accountability, concomitant therapy use and quality of safety and performance data.

7.3 Site Audits

Not applicable. Site audits will be performed at any time during the investigation.

7.4 Case Report Forms (CRFs) and patient diaries

Electronic case report form (eCRF)

The data generated in this trial will be recorded at the study site by the appointed study personnel on a study-specific, validated (as per 21 CFR Part 11) eCRF.

eCRFs will be designed in order to act as a reminder both as far as the timing and the nature of the data to be collected are concerned. The initial (entry) page specified how to fill them in, in agreement with satisfactory regulatory standards.

eCRFs will be designed by an appointed eCRF Designer, using a validated clinical data management system. Access by User ID and password to the eCRFs will be provided to the Investigators together with a User Manual with careful instructions on how to fill them in, in agreement with satisfactory regulatory standards. Training on the use of the eCRF will be performed.

Data entered in the eCRF will be captured by a fully validated system and stored in a dedicated Excel electronic database, which will be used to produce all planned statistical analyses.

In agreement with satisfactory regulatory standards, the investigators, study coordinators, and study monitors will be instructed on the proper use of the electronic eCRF system and will be provided with a user manual with appropriate instructions on software usage, together with individual, private User ID and Password to have access to the eCRF.

The name of personnel authorized to complete an eCRF will be to be given to the assigned study monitor before trial initiation

The eCRF should have been filled-in during or immediately after the conclusion of each visit, preferably within 24 hours but no later than five working days after the visit.

Copy of the eCFR is attached in Annex 2.

Patient diaries

Specific paper patient diaries for the collection of the data pertaining to this clinical trial will be provided to the patients. They will be designed in order to act as a reminder both as far as the timing and the nature of the data to be collected are concerned. The initial page specified how to fill them in, in agreement with satisfactory regulatory standards.

During the study period, patients will be requested to complete a daily diary for the registration of the presence and intensity of upper symptoms, in line with the questions listed in the RSI questionnaire, of the use of rescue medication on an as-needed basis, during the first 6 weeks of treatment and the follow-up phase, and of all possible adverse events or incidents occurred during the study period. At each visit, the Investigator evaluated the data entered in the daily diary and reported them in the eCRF.

7.5 Data Management

As said above, computer systems used for remote data collection and the system for data storing and processing will be validated. Verification and cross-verification of the data entered by the study personnel at each visit will be automatically performed by the system, according to predefined nature/type of the data, value ranges and rules. All rules applied by the system to check specific items will be detailed in a document issued by the Data Management service of the CRO. Queries will be automatically generated by the system for all data found to be inconsistent, incorrect or missing. Queries to be solved/unclear data to be corrected (or confirmed) will be highlighted by the system, to be easily identified by the study personnel when accessing the eCRF website. All changes performed by the Investigator will be tracked by the system.

Once all data will be entered in the eCRF and all outstanding queries will be solved, the Monitor of the study authorized the Investigator to "freeze" the data of the subject's eCRF. No change will be accepted by the system after freezing. Nonetheless, it could have been still necessary to edit additional queries following general quality control checks performed by the Data Manager of the study on the frozen database: in case, queries will be to be edited in paper form and referred to the appropriate hospital/study site personnel, to be resolved with assistance of the study Monitors.

When all data will be received, all data problems will be resolved, all data checks and quality control checks will be performed, and a data review meeting will be held, the trial database will be considered clean and could be locked. After database lock, the appointed statistician performed the statistical analysis as planned. Any further modification of recorded data will be to be documented in a database log form.

The data of all patients, recorded on the eCRFs and on the patient diaries, will be stored in a suitable, properly designed database.

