6 CLINICAL INVESTIGATION PLAN

6.1 Overall Study Design

This will be a phase III, multicentre, prospective, randomised, open-label, two-parallel groups study, followed by a follow-up period.

[figure not shown]
The study plan included a 6-week treatment period, from visit V1 to visit V4, of first-diagnosis patients presenting upper symptoms related to diagnosis of GERD, in the presence/absence of typical symptoms. Patients will be randomised to receive an open-label treatment (in a 1:1 ratio) with Gerdoff®- omeprazole (PPI) (Group 1) or omeprazole (PPI) alone (Group 2). The first administration of investigational products started in the morning of the day following visit V1.

At visit V4, patients in Group 2 who will be treated with omeprazole (PPI) alone, and patients in Group 1 who will be treated with Gerdoff®- omeprazole (PPI) and will be classified as non-responder, completed the study and the most appropriate therapy to treat their symptoms will be prescribed by the investigator.

To assess the maintenance of the effects of treatment, at visit V4 (end of study visit), patients in Group 1 who will be treated with Gerdoff®- omeprazole (PPI) and will be classified as responders could continue with a 12-week follow-up period. During the follow-up period patients could be randomly assigned as open-label (in a 1:1 ratio) to treatment with Gerdoff® or to a control group, which will not receive any treatment. To safeguard the health and well-being of patients, and to keep under control the possible upper symptoms of GERD that could appear, all patients that continued in the follow-up period received omeprazole as rescue medication in a quantity adequate to cover the entire follow-up period. This therapy will be chosen by the study coordinator as it is the treatment commonly used in clinical practice for the treatment of all specific and non-specific symptoms of GERD. The investigator explained to patients that rescue omeprazole could be taken only if necessary and according to the indications given by the Investigator, at constant dosage, and that use will be to be recorded in the daily diary by indicating the reason for administration. The investigator had to report the data in the source documents and in the electronic case report forms (eCRF).

A schematic diagram of the study design follows (Figure 1):

Figure 1. Study diagram

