6.4.8 Blinding and Labelling

Not applicable, as this will be an open-label investigation.

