8.1 Sample Size Justification

Although a search in literature has not identified any published article for trials that used the same investigation design as that used in the present study, some recently published articles (9, 13-15) allowed to formulate a sample size calculation for the present investigation.

The calculation of the sample size will be based on the primary objective of the investigation, i.e. to assess the change of RSI questionnaire from baseline to 6 weeks of treatment in the two treatment arms, Gerdoff®- PPI and PPI alone, based on an hypothesis that the addition of Gerdoff® to PPI could improve the effect of disappearance and of rapidity of control of upper symptoms of GERD. Such effect will be evaluated as the mean change in RSI compared to baseline, taking into consideration the variable age, standard deviation (SD) and expected value after treatment with omeprazole.

The following assumptions will be made for the sample size calculation:

Difference between the two arms (delta): 3.6; SD of the difference: 5.

Based on these assumptions, for a comparison based on unpaired Student t test, at a power of 80% and a level of probability of 5% for a two-tailed test, 62 patients (31 in each treatment arm) will be to be included in the study. Estimating a drop-out rate of 20%, 78 patients (39 in each treatment arm) will be to be included in the study.

The software PS Power and Sample Size Calculations Version 3.0, January 2009, will be used for the sample size calculation.

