8.2 Populations for Analysis

All efficacy and safety analyses will be conducted on the Intent-to-Treat population (ITT), defined as all randomized patients in the first period of study (first 6 weeks) who took at least one study treatment dose.

In addition to the primary analysis carried out on the ITT population, some secondary sensitivity analyses will be carried-out in accordance with the criteria mentioned above. The sensitivity analyses will be implemented according to the following criteria:

- Considering that a minimum intake of study treatment will be required for the assessment of the efficacy of therapy on the primary objective, it will be considered that evaluable patients on the primary end-point had taken at least 95% of the total dosage in the 6-week treatment period, as foreseen in the study protocol. Patients who will not reach this target will be excluded from the primary analysis, but entered in the sensitivity analysis to confirm the efficacy of treatment with Gerdoff® in the improvement of the high symptoms.
- Patients who took not allowed rescue medication will be excluded from the sensitivity analysis on the primary end-point.
- Patients who took drugs that interfere with salivary secretion remained included in the sensitivity
 analyses by derogation from the study protocol, since during the data review meeting the
 clinicians considered as not significant the interference of these drugs on the response of the
 primary variable.
- Patients who had a worsening of the upper symptoms and required an additional therapy or a modification of the dosage of omeprazole taken compared to the protocol during the 6-week

treatment period, according to the Investigator's opinion, will be considered major violators but remained in the study until visit V4 and entered into the ITT efficacy analysis. Such patients will be considered as non-responders in the analysis of the follow-up phase.

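### The data review meeting took at least one analysis-population decision with no masking step described, so the sensitivity analyses, and possibly the primary one, are open to influence by arm and outcome

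*Combined protocol and SAP*

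**What the plan says.** - **Timing.** Section 7.5 (Data Management) sets the order: data received, problems resolved, checks done, then "a data review meeting will be held, the trial database will be considered clean and could be locked". The statistician's analysis follows lock. The section does not mention analysis populations.
- **Masking.** Section 6.4.8 (Blinding and Labelling) reads "Not applicable, as this will be an open-label investigation". Neither 7.5 nor 8.2 says what the meeting's listings show or hide.
- **A decision taken at the meeting.** Section 8.2 (Populations for Analysis) keeps users of drugs that interfere with salivary secretion in the sensitivity analyses. It calls this a derogation from the protocol and gives as the reason that "clinicians considered as not significant the interference of these drugs on the response of the" primary variable. Chronic use of such drugs is exclusion criterion 14 in section 6.3.2 and is not permitted under section 6.4.6.
- **Violator label.** Also in 8.2, patients who worsened and needed extra therapy or a change of omeprazole dose "according to the Investigator's opinion, will be considered major violators". They stay in the ITT efficacy analysis.
- **Primary population.** Section 8.2 puts all efficacy analyses on ITT, meaning randomised with at least one dose taken. It then says that patients below 95% of the scheduled dosage are left out of the primary analysis and enter the sensitivity analysis.

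**The concern.** The RSI is completed by patients who know their treatment. In such a trial the sensitivity analyses carry much of the burden of showing that the primary result is sound. They can do so only if membership was decided without regard to arm or result. When the meeting convenes, the week-6 RSI exists for every patient who provided one, and nothing in the plan keeps it, or the arm, from those deciding. The one decision on record relaxed a written protocol rule, and its stated ground was the response of the primary variable. A reader of the final report could not establish that this decision, or any other taken there, was made without knowledge of the results.

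Open-label treatment does not require an open review. Arm and outcome columns can be withheld from listings whatever patients and investigators knew.

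**Working it through.** **1. What can move, and who moves it**

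| Item in 8.2 | Decided by | Effect on populations |
|---|---|---|
| ITT membership | Fixed rule | None, if the rule is followed |
| Users of saliva-affecting drugs | Data review meeting | Kept in the sensitivity analyses, against the protocol |
| Non-permitted rescue medication | Written rule | Out of the sensitivity analysis |
| Major-violator label | Investigator | Stays in ITT |
| Compliance below 95% | Product counts checked against diary, discrepancies clarified with the patient (6.4.5) | Out of the primary analysis in one sentence, in ITT by another |

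The meeting has one documented decision, and it bears on the sensitivity analyses. The primary analysis is reached mainly through the last row, where two statements in 8.2 conflict.

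**2. The plan's own figures**

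Section 8.1 gives "Difference between the two arms (delta): 3.6; SD of the difference: 5". With two-sided 5% and 80% power:

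n per arm = 2 × (1.960 + 0.842)² × 5² / 3.6² = 30.3, rounded up to 31, or 62 in all.

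With 20% drop-out: 62 / 0.80 = 77.5, rounded up to 78, or 39 per arm.

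Both match the plan. They also show that the 5 is used as the within-arm SD of the RSI change. The concern does not affect the sample size.

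**3. How far selective classification could move a mean**

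The documents give no count of debatable patients, so 6 of 39 in one arm is an assumption. Take RSI change as normal with SD 5, and the 6 as a random subset. The three most extreme expected order statistics of 6 standard normal values are 1.267, 0.642 and 0.202. Setting aside the k worst of the 6 shifts the mean of the remaining patients by

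shift = 5 × (sum of the first k values) / (39 − k)

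- k = 1: 6.336 / 38 = 0.17 points, 4.6% of 3.6
- k = 2: 9.545 / 37 = 0.26 points, 7.2%
- k = 3: 10.553 / 36 = 0.29 points, 8.1%

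With 31 patients in the arm the divisors are 30, 29 and 28, and the shifts are 0.21, 0.33 and 0.38 points. An opposite tilt in the other arm doubles the 39-patient figures to 0.33, 0.52 and 0.59.

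**4. Effect on the error rate**

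These come from simulation with 39 per arm, no true difference and a two-sided t-test at 5%.

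- One arm tilted as in step 3: type I error about 5.3% to 5.5%.
- Both arms tilted in opposite directions: about 6% to 8%.
- Harsher bound, the worst 1 to 4 of a whole arm removed: bias 0.28 to 0.96 points, type I error 6.3% to 15.2%.
- Same numbers removed without regard to outcome: bias about 0, type I error about 5%.

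The last line shows what masked classification protects.

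**The case against.** The strongest reply is that the evidence is narrow. Section 7.5 describes cleaning and lock, not populations. Section 8.2 credits the meeting with a single decision, which retained a whole drug class rather than removing selected patients. The ITT, rescue-medication and compliance rules are written down and leave limited room for judgement. The major-violator label belongs to the investigator, removes nobody from ITT, and would not be touched by masking the meeting's listings. The count of 6 debatable patients has no source, and under it the error rate barely moves when one arm is tilted. Masking would also be imperfect: two sites enrol patients, the arms take different products, and treating clinicians may remember who had what.

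Most of this stands, and it limits the point. A reader might infer that the meeting settles analysis-population status generally, with arm and RSI in view. The documents do not say that: they attribute one decision to the meeting and are silent on what it saw. That the review was unmasked is an inference from the open-label design and the absence of any masking step. Section 8 also refers to a SAP version 1.1 as Annex 10; if that annex describes a masked review, neither 7.5 nor 8.2 reflects it.

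What the reply does not remove is that a protocol rule was relaxed at this meeting, on grounds tied to the primary variable, when outcome data were already in. No safeguard is stated for that decision or for any other the meeting might take.

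**Conclusion.** The point holds in limited form and should be corrected. The sensitivity analyses are open to influence because their membership was partly decided at a late meeting with no masking described. The primary result is exposed only if the compliance exclusion in 8.2 overrides the ITT rule; under ITT alone, neither the meeting's recorded decision nor the violator label changes it.

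The size is modest: about 0.17 to 0.29 RSI points in one arm against a planned difference of 3.6. This assumes 6 debatable patients of 39, SD 5, normal changes, and selection of the worst 1 to 3 of those 6. The harsher bound in the working shows what deliberate selection could do and is not a forecast. It would go too far to infer that the primary result was biased or that patients were selected by outcome. Nothing in the documents shows either, and the one recorded decision excluded nobody.

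**What to change.** In section 8.2, with a cross-reference in 7.5, state that:

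1. The meeting applies the written population criteria using listings without treatment arm, kit or product names, and without post-baseline RSI, Likert and satisfaction scores. Intake appears as per cent of scheduled doses, so that the number of products does not reveal the arm.
2. Each decision is logged with its reason, and the patient-by-patient classification is signed and dated before arm and outcomes are merged.
3. Any later change, and any departure from the protocol criteria, is reported as post hoc. The decision on saliva-affecting drugs would be reported this way.
4. ITT (randomised, at least one dose) is the only primary population, and the 95% compliance rule defines a sensitivity set. This removes the conflict within 8.2, which masking alone would not.

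The cost is a re-cut of the listings and a short SAP revision, with no extra patients, visits or staff. Masking will be partial because treating clinicians may recall the arm, and it does not reach labels that the investigator assigned during the trial. The dated log is useful even so, because it shows what was decided before the results were merged.

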8 STATISTICAL METHODS

The statistical methods will be planned in the protocol and will be then updated, agreed and approved in the final Statistical Analysis Plan (SAP), version 1.1, dated 19 February 2019 (Annex 10).

Statistical analysis will be performed by the statistical department of High Research S.r.l., [name].

8.1 Sample Size Justification

Although a search in literature has not identified any published article for trials that used the same investigation design as that used in the present study, some recently published articles (9, 13-15) allowed to formulate a sample size calculation for the present investigation.

The calculation of the sample size will be based on the primary objective of the investigation, i.e. to assess the change of RSI questionnaire from baseline to 6 weeks of treatment in the two treatment arms, Gerdoff®- PPI and PPI alone, based on an hypothesis that the addition of Gerdoff® to PPI could improve the effect of disappearance and of rapidity of control of upper symptoms of GERD. Such effect will be evaluated as the mean change in RSI compared to baseline, taking into consideration the variable age, standard deviation (SD) and expected value after treatment with omeprazole.

The following assumptions will be made for the sample size calculation:

Difference between the two arms (delta): 3.6; SD of the difference: 5.

Based on these assumptions, for a comparison based on unpaired Student t test, at a power of 80% and a level of probability of 5% for a two-tailed test, 62 patients (31 in each treatment arm) will be to be included in the study. Estimating a drop-out rate of 20%, 78 patients (39 in each treatment arm) will be to be included in the study.

The software PS Power and Sample Size Calculations Version 3.0, January 2009, will be used for the sample size calculation.

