6.3.3 Removal of Patients from Therapy or Assessment

Patient withdrawal

Patients had the right to withdraw from the study at any time for any reason including personal reasons (consent withdrawal). The Investigator also had the right to withdraw any patient from the study if he/she deemed this appropriate and in the best interest of the patients.

The following necessitated the discontinuation of a patient from the study:

- Voluntary subject withdrawal for any reason, even if not motivated;
- Appearance of an adverse event that could put at risk the patient's health;
- Sponsor's decision (to be justified);
- Investigator's decision (to be justified), in the patient's best interest;
- Poor patient's compliance to scheduled study visits and/or study procedures,
- Worsening of clinical general conditions requiring the discontinuation of the study;

- Major protocol violations (e.g. intake of any other therapy for GERD, irrespective of dose and frequency of administration);
- Poor adherence to inclusion/exclusion criteria that emerged after the inclusion of a patient and that will not guarantee the patient's safety.

The reasons for the interruption or the exclusion of a patient from the study had to be reported in the eCRF section 'End of study form' or 'End of follow-up period form' and will be to be communicated to the study sponsor.

In the case of early study discontinuation, the patient will be to be considered as a treatment failure. However, the investigator had to make any effort to perform the end of study assessments, scheduled at visit V4, in case a patient interrupted the study during the 6-week treatment period, or scheduled at visit V6, in case a patient interrupted the study during the 12-week follow-up period.

In the discontinuation visit, the patient had to return the investigational product and the daily diary completed up to the time of discontinuation.

The investigator had to record the reasons for the patient's treatment discontinuation and the early study conclusion in the clinical record/worksheet and in the eCRF. The sponsor had to be timely informed.

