8.3.1 Primary Performance Analysis

In the analysis of primary performance variable, i.e. the mean difference from the baseline (delta) of the RSI score measured after 6 weeks of treatment, the two treatment groups will be compared using a Student's t-test for independent data.

The test results will be tabulated with the appropriate descriptive statistics and with the calculation of the 95% CI of the difference relative to the delta between the two study treatments.

The primary objective of the study will be achieved only if the statistically significant difference between the two study treatments with the current delta value will be coincident with that planned in the calculation of the numerosity, i.e. 3.6.

Sensitivity analyses will be conducted on the primary performance variable. The study of the temporal profile of the RSI questionnaire will be performed using the analysis of variance for repeated measures (ANOVA). In addition to the treatment effect, the time effect and the treatment by time interaction will be included in the model.

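### The 80% power in Section 8.1 assumes dropouts leave the test; it makes no allowance for dilution under the ITT primary analysis named in Section 8.2, where power is about 71% if dropouts stay in with no treatment effect

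*Combined protocol and SAP*

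**What the plan says.** Section 8.1 (Sample Size Justification) gives the planning values as "Difference between the two arms (delta): 3.6; SD of the difference: 5". It then states the requirement: "at a power of 80% and a level of probability of 5% for a two-tailed test, 62 patients (31 in each treatment arm". The allowance for losses follows: "Estimating a drop-out rate of 20%, 78 patients (39 in each treatment arm) will be to be included in the study".

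Section 8.3.1 (Primary Performance Analysis) describes the test on the RSI change at 6 weeks: "the two treatment groups will be compared using a Student's t-test for independent data".

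Section 8.2 (Populations for Analysis) defines who is analysed: "All efficacy and safety analyses will be conducted on the Intent-to-Treat population (ITT), defined as all randomized patients in the first period of study", provided that at least one dose was taken. Its next paragraph again calls the ITT analysis the primary one. A later bullet in the same section says something different: patients who took less than 95% of the scheduled 6-week dosage are left out of the primary analysis and enter a sensitivity analysis instead.

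On patients who stop early, Section 6.3.3 says: "In the case of early study discontinuation, the patient will be to be considered as a treatment failure". Note (c) to the Figure 2 flow-chart repeats this. Both also ask the investigator to try to carry out the V4 assessments at early exit. The text available gives no RSI value for such a failure and no rule for a missing week-6 RSI.

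**The concern.** Two parts of the plan treat the same 20% of patients differently. In Section 8.1 they vanish from the test and are replaced by over-recruitment. Under the ITT definition in Section 8.2 they stay in. Patients who stop treatment and are regarded as failures would be expected to show less of the added benefit of the device. Keeping them pulls the mean difference below 3.6, and mixing them with completers may also change the SD.

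At stake is how the result is read. A non-significant ITT comparison would be taken as evidence against a hypothesis tested with 80% power, when the chance of detecting the planned effect could be noticeably lower. The opposite error is also possible: if the analysis actually run omits discontinuers, the 80% is about right, but the analysis is not the ITT analysis announced.

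**Working it through.** **Inputs from the documents.** Difference 3.6, SD 5, two-sided 5%, 80% power, 20% dropout, 31 then 39 per arm (Section 8.1); 1:1 allocation (Section 6.1); unpaired t-test (Section 8.3.1). SD 5 is used as the common SD of the change within each arm, the reading that reproduces the printed 31.

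**Assumptions added here.** Dropout is 20% in each arm, and every randomised patient takes at least one dose.

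**Step 1: reproduce the plan.**
- n per arm = 2(1.960 + 0.842)² × 5² / 3.6² = 30.3, rounded up to 31, so 62 in total.
- Inflation: 62 / (1 − 0.20) = 77.5, rounded up to 78, or 39 per arm.
- Power at 31 per arm: noncentrality 3.6 / (5√(2/31)) = 2.84 on 60 df, giving 79.6%.

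The printed figures reproduce. Letting the number of completers vary binomially (39 per arm, 80% retained) gives 79.7%, so the 80% is the power of a test that omits the dropouts.

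**Step 2: keep the 20% in the test with no between-arm effect.**
- Expected difference: 0.8 × 3.6 + 0.2 × 0 = 2.88.
- With SD held at 5: noncentrality 2.88 / (5√(2/39)) = 2.54 on 76 df, giving 70.9%.

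**Step 3: let dropouts keep a fraction f of the effect, SD 5.** The difference is 3.6 × (0.8 + 0.2f), at 39 per arm.

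| f | Difference | Power |
|---|---|---|
| 0 | 2.88 | 70.9% |
| 0.25 | 3.06 | 76.1% |
| 0.5 | 3.24 | 80.7% |
| 1 | 3.60 | 88.1% |

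If dropouts at f = 0.5 also show only half of the mean fall, the mixture SD rises to 5.15, 5.25 or 5.54 for assumed control-completer falls of 4, 6 or 10 points. Power is then 78%, 77% or 72%.

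**Step 4: score every dropout as no change from baseline (illustration only).** With control-completer mean fall m, the treated-completer mean is m + 3.6. Each arm's variance is 0.8 × 25 + 0.16 × (mean)², and the difference is 2.88. For example, at m = 4 the variances are 20 + 0.16 × 16 = 22.56 and 20 + 0.16 × 57.76 = 29.24, average 25.90, SD 5.09.

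| Assumed m | SD | Power |
|---|---|---|
| 4 | 5.09 | 69% |
| 6 | 5.50 | 63% |
| 8 | 5.99 | 55% |
| 10 | 6.54 | 48% |

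Simulation of 20,000 trials per setting agreed to within about one percentage point. The documents give neither m nor the no-change rule.

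**The case against.** The strongest reply is that the plan never says that discontinuers enter the continuous primary analysis without benefit. Being counted as a failure has a defined use only for the responder endpoint in Section 8.3.2, and the effort to obtain V4 assessments at exit suggests that a measured RSI is wanted. Patients measured at exit may keep part of the effect, and Step 3 shows that keeping half, with SD 5, already gives about 81%. This stands. It rules out saying that the 80% holds only for completers, or that 71% is a ceiling.

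Second, the 95% dosage bullet in Section 8.2 would remove nearly every discontinuer from the primary analysis: 95% of 42 days is 39.9 days, so a patient who stops by day 39 falls below it. On that sentence the calculation in Section 8.1 is close to what would be run. This also stands as far as it goes, but the bullet conflicts with the two ITT statements in the same section, so it cannot by itself settle which analysis is primary.

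Third, 3.6 might be meant as the difference among all analysed patients, in which case nothing is diluted. The document does not say. But with everyone retained at 3.6, the 20% inflation would be unnecessary (39 per arm gives 88%). The inflation itself shows that Section 8.1 expects to lose those patients from the test.

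A reader might infer that the written primary analysis has power of 48% to 71%. The documents do not support that range. Its lower end needs both a no-change scoring rule and a 10-point control fall, and neither is in the plan.

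**Conclusion.** The point holds in a limited form. The arithmetic in Section 8.1 is correct, but its 80% belongs to a test on 62 evaluable patients who show the full 3.6 points. It does not allow for dilution under the ITT analysis that Section 8.2 names as primary.

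The figure closest to the plan's own inputs is about 71% at 39 per arm. It rests on 20% dropout in both arms, no between-arm effect in dropouts and SD 5: a loss of about 9 percentage points (79.6% to 70.9%). No single ITT power can be asserted, because the plan does not fix what a discontinuer contributes to the t-test. The results in Steps 3 and 4 are conditional scenarios, and those in Step 4 are illustrations only.

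These are powers of the t-test alone. Section 8.3.1 also ties success to the observed difference matching 3.6, and that condition is not evaluated here.

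**What to change.** Keep 78 patients and make three text changes.

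1. In Section 8.1, label the 80% as the power for 62 evaluable patients with a full 3.6-point difference. Add that, with 20% discontinuation retained in the ITT test and no treatment effect in those patients, the expected difference is 2.88 and power at 39 per arm is about 71% with SD 5. Show any other scenario with its assumptions stated.
2. In Section 8.2, reconcile the ITT primary analysis with the bullet that excludes patients below 95% dosage from the primary analysis, so that one population is primary and the other is a sensitivity analysis.
3. In Section 8.3.1, state what week-6 RSI change a discontinuer receives in the t-test, with and without an exit assessment. If SAP version 1.1 (Annex 10 of the protocol) already contains such a rule, carry it into this section.

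Items 2 and 3 should be settled first, so that the power stated under item 1 matches the analysis that will be run. The cost is a few sentences in the protocol and SAP. The downside is a less favourable stated power if discontinuers are retained.
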